3.5.3 Identifying, informing and consenting patients

The procedure for informing and consenting patients will be the same in all centres and devised to accommodate local variations in the patient pathway. (See Appendix 1 for arrangements at Papworth.) The local investigator will make the initial approach to the patient. The Trial Coordinator or local research nurse will provide any further information subsequently and take written consent.

The following scenario will be adopted at Papworth: the surgeon will outline the study to eligible patients at a routine surgical clinic and provide them with a simple summary to take home. The trial coordinator (or research nurse) will contact patients at home to ask whether they would be interested in participating. If patients agree, the trial coordinator/research nurse will post further information and the patient information sheet and consent form to their home.

When patients attend the pre-admission clinic (approximately 1 month before their surgery) the trial coordinator/research nurse will go through the trial in detail and answer any questions. The surgeon will also be available to provide further information if necessary. If patients are still willing to participate the trial coordinator/research nurse will confirm eligibility and obtain written informed consent.

Once consent has been obtained patients will be trained in the use of the 4-day ECG recording device and will use it at home to monitor their heart rate for 4 days.

3.5.4 Blinding

Patients themselves, any researchers collecting Health-related Quality of Life data and cardiologists assessing the 4-day ECG results will be unaware of the group to which the patient has been allocated.

The Patient Information Sheet (PIS) will state clearly that the patient will not know whether or not they have had the adjunct maze procedure. However the PIS will also explain that the patient can be un-blinded for medical reasons but that they will still be followed up and remain part of the trial.

Blinding of the patient is essential because the primary outcome is patient benefit. However this is unlikely to be successful if details of the patient's operation are fully accessible in their notes. On the other hand this information must not be held too securely because the patient could be at risk if details are not immediately available if required for medical reasons.

The following strategy will be adopted to accommodate these requirements: Patients' medical notes will be labelled to indicate that they are participating in the Amaze trial. Routine reports will provide details of their elective surgery but will only state that the patient was randomised within the Amaze trial. Notes describing the research intervention (ie the adjunct maze procedure or no trial-related surgery) will be placed in a sealed envelope entitled ' The Amaze Trial ' and kept in the patient's notes. Clinicians will be able to access this information should a medical need arise. The Trial Management Protocol will include details of this ' unblinding protocol '.

4. INTERVENTION

4.1 Randomisation

Eligible patients who fulfil the inclusion criteria, have provided full written consent and have had sufficient time for discussion and consideration, will be randomised (in a 1:1 ratio) to one of two groups. They will receive either their routine cardiac surgery with no additional procedure or their routine cardiac surgery with an adjunct maze procedure.

Patient allocations will be computer generated by the trial statistician and will be in random permuted blocks of variable lengths, stratified by surgeon and by planned cardiac procedure (CABG, aortic valve, mitral valve, combined procedure).

On the day of surgery, when the patient is in the anaesthetic room, the local centre will register the participating patient with Papworth Hospital R&D Unit by telephone or fax.

Patient details, surgeon and planned cardiac procedure will be recorded by R&D unit staff not otherwise directly involved with the trial. Once registration is complete the group allocation will be released to the surgical team who will also be responsible for completing the surgical data forms. The group allocation will not be made available to any other staff who are directly involved with the trial.

4.2 Control intervention

Patients randomised to the control arm will receive their pre-operative management, elective cardiac surgery (without an adjunct maze procedure) and post-operative management according to standardised hospital protocols. All subsequent management, follow up and data collection will be identical to the experimental intervention group.

4.3 Experimental intervention

Patients randomised to the experimental arm will receive their pre-operative management and elective cardiac surgery as described in the protocols. During the operation, the surgeon will also conduct the adjunct maze procedure using the agreed standardised protocol. Investigators will use the ablation device in routine use at their institution. The procedure will be fully defined in the Trial Management Protocol. Post-operative management and subsequent follow-up and data collection will be identical to the control group.

4.4 Standardisation between centres:

In order to minimise potential confounding by other components of the patient's care the following aspects of the trial will be standardised at all the collaborating centres. The agreed protocols will form part of the Trial Management Protocol for this study.

4.4.1 Management of patients before, during and after surgery

This will be undertaken according to the local site's normal practice irrespective of randomisation. The only exceptions will be processes required to maintain blinding of the patient, cardiologist and quality of life interviewer, which will be described in the Trial Management Protocol.

4.4.2 Conducting and reporting on the adjunct maze procedure $^{(14)}$ and defining the prescribed lesion set $^{(6)}$

Clinicians are free to carry out the lesions that they would perform in normal practice. Details of the ablation procedure and all lesions will be documented. The full lesion set is illustrated in Figure 1.

Recently published guidelines for reporting data and outcomes for surgical treatment of atrial fibrillation ⁽¹⁴⁾ will be followed.

4.4.3 Post-operative drugs

i. Amiodarone – unless contraindicated 200mg tds reducing over 3 weeks to 200 mg per day for 6 weeks. The drug will be stopped if stable sinus rhythm (SR) is established at 6 weeks. Further prescription after this period will be based on individual clinical judgement. Details will be fully documented.

ii. Warfarin – will be prescribed until the patient is in stable SR. After this, centres will adopt their normal practice. Details will be fully documented.

iii. β Blockers – will be prescribed according to individual clinician's judgement. Details will be fully documented.

iv. Other drugs – will be prescribed according to individual clinician's judgement. Cardiac drugs with anti-arrhythmic, anti-hypertensive and anti-coagulant actions, including aspirin and warfarin, will be documented.

4.4.4 Indications for cardioversion, timing and number of attempts

The protocol does not require cardioversion to be carried out at discharge but if it is performed for clinical reasons the details must be recorded. If the patient is in AF at the time of the first follow-up appointment cardioversion must be attempted no later than 3

Version no: 3.0 date: 9 October 2009

months after surgery. If cardioversion is unsuccessful it should be attempted again at about 6 months after surgery.

5. OUTCOME MEASURES

5.1 Primary outcomes:

i) Return to SR at 12 months

The number of patients in SR at 12 months after surgery will be determined by 4-day ECG monitors that will be provided for patients to wear continuously for 4 days at 12 months after their operation.

ii) Clinical effectiveness - quality-adjusted survival over 2 years

Clinical effectiveness will be measured by QALYs, which will be calculated by combining length of survival and the EQ-5D (administered at randomisation, on discharge and at 6 weeks and 6, 12 and 24 months after the procedure).

5.2. Secondary outcomes:

- (i) Clinical endpoints of SR at 24 months after surgery, overall survival and stroke-free survival, incidence of anticoagulant-related haemorrhage.
- (ii) Health-related quality of life measured by the EuroQoL, SF-36 & NYHA (for breathlessness)
- (iii) Resource use and cost-effectiveness of the adjunct maze procedure.
- (iv) Anticoagulant and antiarrhythmic drug usage.

6. DATA COLLECTION

6.1 Methods

The data will be collected on to a web-based system designed and coordinated by the Data Scan and Quality Officer at Papworth Hospital. He will be responsible for training researchers to use the system and will conduct initiation visits. The Clinical Research Nurse (CRN) at each centre will enter the data directly on to the database or enter the data manually on to the printed form until such time as it can be entered directly. Surgical data will be recorded by a designated member of the surgical team either directly or via a paper form. All paper data collection forms will be returned to the R&D Unit at Papworth. The Trial Coordinator (TC) will be responsible for training the CRNs and other data collection staff in each hospital, and for data monitoring and quality control. Data audits (to be designed) will be carried out by the Trial Coordinator at 3-6 month intervals depending on the recruitment and activity rates. The whole process will be overseen by the Trial Manager situated in the co-ordinating centre at Papworth Hospital.

6.2 Baseline data collection

We will adhere to the ACC/AHA/ECS 2006 Guidelines ⁽¹⁵⁾ which recommend that the initial patient description includes demographics, type and duration of AF and the planned cardiac procedure.

The first 4-day ECG recording will start after the patient attends the preadmission clinic and has consented to participate. All other baseline measurements will be recorded on the day of admission for surgery. Once these measurements have been taken the participating patient with be registered with the co-ordinating centre's R&D unit and then randomised as described in 4.1.

6.3 Data collection during and after surgery

(See Appendix 3 for the Schedule of Events and Appendix 4 for the full list of data to be collected.)

Data collection will be based on the recommendations of Shemin et al ⁽¹⁴⁾ and include procedural details – including the lesion set in the experimental group.

Version no: 3.0 date: 9 October 2009

Data to be collected after surgery will include: mortality, stroke/thromboembolic events, medications, EuroQoL, health-related quality of life, cardioversion plan if appropriate, 4-day ECG recordings, resource use, adverse events.

Data will be collected during surgery, at discharge, 6 weeks after surgery (at a routine service visit), at 6, 12 and 24 months after surgery during out-patient research visits and annually thereafter by telephone follow-up.

6.4 Analysis of ECG recordings

All 4 day continuous ECG recordings will be analysed centrally at Papworth Hospital. Participating centres will be requested to forward the SD cards from the ECG recorders to Papworth Hospital. Analysis of this data using the proprietary automated software package, together with manual checking of the recording in its entirety, will be done. Total time spent in sinus rhythm and in AF (AF burden) during the 4 day recording will be calculated, with only those episodes of AF lasting greater than 60 seconds duration included in the analysis. Episodes of atrial flutter will be noted and included in the AF burden.

6.5 ONS tracking

All patients enrolled in this trial (with their consent) will be registered with the Office of National Statistics (ONS) Tracking System to allow long term follow up of survival.

7. STATISTICAL & ECONOMIC ANALYSES

7.1 Statistical analysis

All statistical analyses and reporting will comply with CONSORT guidelines ⁽¹³⁾ where possible. For the intermediate primary outcome, return to SR at 12 months, all patients with 4-day ECG results at 12 months will be included in the analysis according to the group to which they were randomised. Secondary analyses will consider a Complier Average Causal Effect analysis ⁽¹⁸⁾ and assessment of sensitivity of results to a range of assumptions regarding missing data. Results will be summarised as the number and percentage in SR and compared using Likelihood Ratio Tests. QALYs will be estimated from serial measurements of the EQ-5D for each patient up to 2 years using interpolation (see economic analysis below).

Secondary outcome measurements will be analysed in a similar way to the above, but will include only those patients for whom measurements were available. Time to all cause death will be explored using Kaplan-Meier curves. Health related quality of life scores and the EQ-5D utility score will be compared using Likelihood Ratio Tests from linear regression models including baseline levels and treatment group.

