3.5 Recruitment

3.5.1 Sample size

The primary outcome includes a purely clinical end point as well as an outcome of importance to patients.

It consists of: 1) return to sinus rhythm (SR) at 12 months and 2) clinical effectiveness measured as quality-adjusted survival over 2 years. Sample size calculations are based on both these primary endpoints.

1) Return to SR at 12 months.

Published RCTs of ablation as an addition to cardiac surgery have reported rates of return to SR at 12 months ⁽⁸⁻¹²⁾ ranging from 44% to 87% in the trial arms and 5% to 33% in the control arms. If we take a conservative estimate of the difference between the groups (45% vs. 30%) then we would have 80% power to detect this difference with a sample size of 176 in each group, total 352 (2-sided significance 5%). With recruitment of 400 patients this would allow for deaths or loss to follow up at 12 months of approximately 15%.

2) Clinical effectiveness measured as quality-adjusted survival over 2 years.

The emphasis in cost-effectiveness studies is on estimation rather than hypothesis testing so that formal sample size calculations are less important. However, we provide a power calculation based on the effectiveness measure QALY. We could find no studies reporting comparative QALYs in similar patients undergoing ablation and cardiac surgery. From previous studies of patients undergoing angiography for suspected ischaemic heart disease ⁽¹⁶⁾ and patients with refractory angina ⁽¹⁷⁾ the standard deviation of QALYs over 12 and 18 months is at most 0.3. Over follow up of 2 years the minimum clinically important improvement is considered to be one extra month of quality-adjusted life, or 0.083 QALYs. With a sample of 200 patients per group, total 400, we would have approximately 80% power to detect a difference of 0.083 QALYs, (2-sided significance 5%). If the accepted threshold for cost effectiveness were in the range £20-30,000 per QALY and we could demonstrate a significant increase in QALYs of 0.0833, then the procedure would be cost-effective for an incremental cost of at most £2,500.

3.5.2 Feasibility of proposed recruitment:

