7.1.1 Sub-group analyses

Sub-group analyses will investigate the variation in treatment effects between:

- i. patients with paroxysmal and non-paroxysmal AF,
- ii. individual centres,
- iii. different ablation devices,
- iv. complete and incomplete lesion sets,
- v. different cardiac surgical procedures.

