The QALYs experienced by each patient to 24-months post randomisation will be calculated as the area under their utility curve to 24-months or time of death, whichever occurs first. In order to adjust for differences in baseline utilities a linear regression will be fitted to the utilities post treatment, with baseline utility and treatment group as explanatory variables. Treatment effects will be taken from the treatment group coefficient of this regression. For patients who do not complete all EuroQoL/resource use measurements and are censored the methods of Willan and Lin ⁽²³⁾ will be used to estimate mean QALYs and costs.

The incremental cost-effectiveness ratio (ICER), calculated as the ratio of the difference in costs and QALYs, will be estimated using the sample means. In order to generate confidence intervals without assuming any parametric form for the distribution of the costs, bootstrapping will be used to resample patients and repeat the calculations described above 1000 times. ⁽²⁴⁾ Measurements will be summarised as the mean and 95% confidence interval, estimated using bootstrapping. The bootstrap samples for the treatment comparison will also be plotted on the cost-effectiveness plane. In addition, cost-effectiveness acceptability curves (CEAC) for these comparisons will be plotted. The CEAC plots the probability that a functional test is cost-effective if we are willing to pay at most $\pounds X$ per QALY on the vertical axis, against X on the horizontal axis. Sensitivity analysis will be used to explore the impact of the deterministic variables within the economic analysis (e.g. unit cost estimates discount rate).

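### Randomisation is stratified by surgeon and planned procedure, but the stated QALY and quality-of-life regressions leave both out, so their standard errors are somewhat too large and a little power is lost

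*Protocol*

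**What the plan says.** Section 4.1 allocates patients 1:1 in permuted blocks of variable length, "stratified by surgeon and by planned cardiac procedure (CABG, aortic valve, mitral valve, combined procedure").

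The analysis is described in three places:

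- **Utility and QALYs (section 7.2, Economic Analysis).** Post-treatment utilities are regressed "with baseline utility and treatment group as explanatory variables", and the treatment effect is the treatment coefficient of that regression. Quality-adjusted survival over 2 years is one of the two primary outcomes (sections 3.5.1 and 5.1).
- **Quality-of-life and EQ-5D scores (section 7.1).** These are "compared using Likelihood Ratio Tests from linear regression models including baseline levels and treatment group".
- **SR at 12 months (section 7.1).** "Results will be summarised as the number and percentage in SR and compared using Likelihood Ratio Tests". No model is named, and no covariate is listed or ruled out.

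Procedure and centre appear elsewhere only as subgroup factors, as does the contrast between "patients with paroxysmal and non-paroxysmal AF" (section 7.1.1). A baseline rhythm recording exists: "The first 4-day ECG recording will start after the patient attends the preadmission clinic" (section 6.2).

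**The concern.** Stratified blocks remove differences between strata from the treatment contrast. A linear model without the strata leaves that variation in its residual. Its standard error then describes a less precise trial than the one that was run: intervals are too wide and the test rejects less often than 5% under the null. Listing procedure and centre as subgroup factors does not repair this, because a subgroup analysis examines variation in the treatment effect and does not adjust the main comparison.

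The linear models are where the protocol actually names its covariates. One of them carries a primary outcome whose sample size has no slack: the stated QALY power of about 80% requires all 400 patients.

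**Working it through.** **Inputs from the protocol (section 3.5.1).** QALY standard deviation (SD) 0.3, difference 0.083, 200 per arm, two-sided 5%. SR 45% v 30%, 176 per arm, 80% power.

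**Reproducing the plan's figures.**

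- QALY: standard error (SE) = 0.3 × √(2/200) = 0.030 and 0.083/0.030 = 2.767, so power = Φ(2.767 − 1.96) = 79.0%. This matches the stated approximate 80%.
- SR: the pooled two-proportion formula gives 163 per arm, and with a continuity correction 176, the stated figure. A likelihood ratio test uses no such correction. The uncorrected normal approximation gives 83.1% power at 176 per arm and 81.8% at 170 per arm (400 × 0.85 / 2).

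**Effect of leaving out the strata (QALY).** The protocol gives no figure for how prognostic the strata are. Let R² be the share of the variance left after baseline utility that surgeon and procedure explain. Assume balanced strata, and take 0.3 as the SD after baseline adjustment. Then:

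- model SE / true SE = 1/√(1 − R²)
- true size of the unadjusted test = 2[1 − Φ(1.96/√(1 − R²))]
- true power, unadjusted = Φ((2.767 − 1.96)/√(1 − R²))
- power, adjusted = Φ(2.767/√(1 − R²) − 1.96)

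| R² (assumed) | SE too large by | True size | Power, unadjusted | Power, adjusted |
|---|---|---|---|---|
| 2% | 1.0% | 4.8% | 79.2% | 79.8% |
| 5% | 2.6% | 4.4% | 79.6% | 81.0% |
| 10% | 5.4% | 3.9% | 80.2% | 83.1% |
| 20% | 11.8% | 2.8% | 81.7% | 87.1% |

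Worked for 10%: √0.9 = 0.949. Unadjusted power is Φ(0.807/0.949) = Φ(0.850) = 80.2%. Adjusted power is Φ(2.767/0.949 − 1.96) = Φ(0.956) = 83.1%.

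**How balanced the strata can be.** Eight centres with one or more surgeons each (section 3.2) and four procedures give at least 8 × 4 = 32 strata, or at most 400/32 = 12.5 patients per stratum on average. With an assumed 20 surgeons there are 80 strata and 5 patients in each. Many blocks would stay incomplete, so the table is an upper limit on the effect for each R².

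**SR, by simulation.** Assumptions, none from the protocol: 352 patients with outcome, 20 surgeons, blocks of 2 and 4, a procedure log-odds scale of log 2 to log 4, surgeon SD 0.3 to 0.5 on the log-odds scale, 25% paroxysmal AF with odds ratio 2 to 8, and overall rates of 45% v 30%. There were 1,500 trials per scenario, so the simulation standard error of a 5% size is √(0.05 × 0.95/1500) = 0.6 points.

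| Logistic likelihood ratio test | Power | Size under the null |
|---|---|---|
| Treatment only | 82–85% | 4.1–5.1% |
| + procedure, surgeon dummies | 84–89% | 5.6–6.2% |
| + AF type | 87–92% | 5.7–6.1% |

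The unadjusted standard error of the risk difference was at most about 4% too large. Part of the adjusted power is not real: 19 surgeon dummies pushed the size above 5%.

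**The case against.** The strongest reply concerns SR. A likelihood ratio test from an adjusted logistic regression fits the section 7.1 sentence as it stands, and the covariates of such a model are commonly settled in a statistical analysis plan, which is not available here. This stands: silence is not exclusion, and the protocol makes no error on SR.

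A reader might also infer that omitting AF type and baseline rhythm invalidates the SR standard error. It does not. Neither is a stratification factor, so chance imbalance in them is already covered by the test's error rate. Adjusting for them would add power, and in a logistic model this comes through a larger conditional effect, not a smaller standard error of the log odds ratio.

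Further points in the plan's favour:

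- The error is conservative. There is no bias and no added false-positive risk.
- Section 3.5.1 itself puts estimation ahead of testing for QALYs. That lowers the stakes of the lost power, but intervals that are too wide affect estimation as well.
- In section 7.1 the quality-of-life models are described as including two terms, which is not clearly a closed list. The section 7.2 wording is firmer, and it governs a primary outcome.
- Every R² above is assumed, and it must be variance left over after baseline utility.

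**Conclusion.** The point holds for the utility/QALY regression and, with the small doubt about wording just noted, for the quality-of-life models. Followed as written, they give conservative standard errors and lose a little power. At an assumed residual R² of 2% to 20% with balanced strata, the QALY standard error is 1% to 12% too large and true size is 4.8% to 2.8%. The power forgone runs from under 1 point (79.2% v 79.8%) to about 5 points (81.7% v 87.1%). Sparse strata make all of this smaller.

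At R² = 10% it is tempting to set the adjusted 83.1% against the nominal 79.0%. The right comparator is the unadjusted test's true power of 80.2%, so the gain is about 3 points.

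For SR the protocol is silent, and at its assumed rates an unadjusted test keeps the planned 80% power. The documents do not support a claim that the SR analysis is invalid or underpowered on this account.

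**What to change.** - **Utility/QALY and quality-of-life regressions:** add planned procedure as a fixed effect, in the categories used for stratification, and surgeon as a random intercept. Use centre instead if surgeon strata are too sparse. Avoid a dummy for each surgeon. Carry the adjusted regression through the bootstrap repetitions.
- **SR:** state that the likelihood ratio test comes from a logistic model with treatment and the same stratification factors, and report the unadjusted numbers and percentages alongside.
- **Optional for SR:** pre-specify AF type and rhythm on the baseline 4-day ECG as covariates, described as a gain in power.

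The cost is wording and minor programming. Surgeon and planned procedure are recorded at registration, and AF type and the ECG at baseline, so nothing new is collected. Fixing the list before unblinding also removes any later choice of covariates.

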Appendix 3 Summary schedule of events

Data collected	Baseline	Procedure	Discharge	6 weeks (routine)	6 mos	12 mos	24 mos	Annual
HRQoL (SF- 36, NYHA)	Х			Х	Х	х	Х	Х
EQ-5D	Х		Х	Х	Х	Х	Х	Х
Angina class (CCS score)	Х							
Procedural data		х				X		
Stroke diagnosis & stroke-specific quest.				x	x	x	х	х
Mortality		х		X	Х	Х	Х	Х
Medication	Х		х	Х	Х	Х	Х	Х
4-day ECG	Х					Х	Х	
Resource use		Х	x	Х	Х	Х	Х	Х
Adverse events		×	x	Х	х	х	х	х

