Appendix 4: Data to be collected

Stage of trial	Data to be collected				
i. Baseline screening prior	Confirmation of eligibility and adherence to				
to consent	inclusion/exclusion criteria				
ii. Baseline post consent	 Basic demographics Symptoms & severity, including angina class, NYHA class and palpitations Type and duration of AF Current medication Details of previous attempts at cardioversion (consistent) 				
	 with ACC/AHA/ECS 2006 Guidelines) EuroSCORE Underlying cardiac disease including coronary lesions, valve lesions and ventricular function Details of planned operation Baseline HRQoL (EuroQoL, SF-36 & NYHA) 4 day ECC 				
iii. Peri-procedural	 4-day ECG Detailed operative data Ablation device used (in intervention group) Details of lesions used (in intervention group) Immediate post-operative electrocardiogram (ECG) Mortality, morbidity, length of stay Resources (theatre time, device costs, consumables, length of stay in ICU and cardiac ward) 				
iv. At discharge	 ECG Cardiac medication, including anticoagulants and antiarrhythmics Any pacemaker implant EuroQoL Resource use Adverse events 				
v. 6 weeks post-surgery (routine clinic visit)	 Stroke diagnosis and stroke specific/thromboembolic event questionnaire Mortality Details of medication (anticoagulant,antiarrhythmic) Cardioversion plan if appropriate EuroQoL Resource use Adverse events 				
vi. 6 months post-surgery	 Details of medication (anticoagulant, antiarrhythmic) Stroke diagnosis and stroke specific questionnaire/thromboembolic event Mortality HRQoL (EuroQoL, SF-36 & NYHA questionnaires) Details of any cardioversion and outcome Details of any pacemaker insertion Resource use Adverse events 				
vii. 12 & 24 months post- surgery	 Details of medication (anticoagulant, antiarrhythmic) Stroke diagnosis and stroke specific and thromboembolic event questionnaire. Mortality HRQoL (EuroQoL, SF-36 & NYHA questionnaires) Details of any cardioversion and outcome Details of any pacemaker implant 4-day ECG monitoring Resource use 				

Version no: 3.0 date: 9 October 2009

	Adverse events
iix. Annually (by telephone – funding not requested)	 Details of medication (anticoagulant, antiarrhythmic) Stroke diagnosis and stroke specific questionnaire/thromboembolic event
	 Mortality HRQoL (EuroQoL, SF-36 & NYHA questionnaires) Details of any cardioversion and outcome Details of any pacemaker insertion Resource use Adverse events

Version no: 3.0 date: 9 October 2009 Page 25 of 39

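### Secondary quality-of-life comparisons are specified as available-patient regressions on baseline and arm, leaving earlier post-surgery visits unused; a repeated-measures model is a cheap improvement.

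*Protocol*

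**What the plan says.** Protocol section 7.1 fixes two things for the secondary outcomes. The first is the analysis set: the analysis "will include only those patients for whom measurements were available". The second is the model, which covers both the quality-of-life scores and EQ-5D utility and rests on "Likelihood Ratio Tests from linear regression models including baseline levels and treatment group". It names no visit term, within-patient correlation or imputation for these outcomes.

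The measures are longitudinal. Section 6.3 has data collected at discharge, at 6 weeks, and "at 6, 12 and 24 months after surgery during out-patient research visits and annually thereafter by telephone follow-up". Section 5.1 and Appendix 3 put EQ-5D at discharge, 6 weeks, and 6, 12 and 24 months, which is five post-baseline assessments to 24 months. SF-36 and NYHA fall at 6, 12 and 24 months. Appendix 3 also shows them at 6 weeks, where Appendix 4 lists only EuroQoL.

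Section 5.2 gives one secondary outcome as "Health-related quality of life measured by the EuroQoL, SF-36 & NYHA (for breathlessness". Appendix 3 puts SF-36 and NYHA in one row, and Appendix 4 lists the baseline symptoms as "including angina class, NYHA class and palpitations". No separate method for NYHA is named.

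Missing data are handled explicitly elsewhere. Section 7.1 plans sensitivity analyses in the paragraph on sinus rhythm at 12 months. Section 7.2 uses inverse weighting for censored patients, but for mean QALYs and costs.

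**The concern.** A regression with only baseline and arm, fitted to patients who have the measurement, draws on nothing between baseline and the visit analysed. A patient with 6- and 12-month scores but no 24-month score then adds nothing to the 24-month comparison.

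That is harmless if missingness depends only on baseline and arm. It is not harmless if patients who feel worse after surgery stop returning questionnaires and this happens differently in the two arms. The patients who remain are then no longer comparable, although the trial already holds the earlier scores that would correct for this.

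The bias in the 24-month SF-36 and EQ-5D contrasts is the main matter, with a small loss of precision. A lesser matter is that an ordinal class sits in a group of outcomes whose only named method is linear regression.

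**Working it through.** The protocol gives no figure for this point, so there is none to reproduce. The check measures how large the bias could be.

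**Inputs from the protocol**
- Loss: the note to Appendix 2 expects 15% (5% deaths plus 10% without primary outcome data). The Appendix 2 totals give 360 of 400 at 24 months, a 10% loss. I used 10% and 15%.
- Patients per arm at 24 months: 360 / 2 = 180 (1:1 allocation, section 4.1).

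**Assumptions not in the protocol**
- Scores have SD 1 at each visit, and the 12- and 24-month scores correlate 0.5 to 0.7.
- Drop-out before 24 months depends on the 12-month score in the control arm only, with log-odds 0.5 or 1.0 per SD, lower scores leaving more often. In the other arm the same fraction is lost at random.
- The true effect is zero.

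**Standard error for scale:** sqrt[(2/180) × (1 − r²)], where r is the correlation of baseline with the 24-month score. This gives 0.105 (r = 0), 0.097 (r = 0.4), 0.091 (r = 0.5) and 0.075 (r = 0.7).

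**Bias.** Two million patients were simulated per scenario. The available-patient model regresses the 24-month score on baseline and arm. The likelihood estimate also uses the 12-month score.

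| Baseline correlation / 12-to-24-month correlation | Bias of available-patient model (SD) | Standard error (SD) |
|---|---|---|
| 0.5 / 0.5 | 0.01 to 0.03 | 0.091 |
| 0.7 / 0.7 | 0.01 to 0.03 | 0.075 |
| 0.4 / 0.6 to 0.7 | 0.02 to 0.07 | 0.097 |
| 0 / 0.6 | 0.03 to 0.08 | 0.105 |

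Each range covers both loss rates and both log-odds. The direction is against the ablation arm, because the control patients who remain look too well. The extreme corner (baseline unrelated to later scores, correlation 0.7, 15% loss, log-odds 1.0) reaches 0.09 and is still below its standard error of 0.105. The likelihood estimate was within 0.003 of zero throughout, which is simulation error. With the same drop-out rule and rate in both arms, the available-patient bias was also about zero.

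**Precision at 24 months.** Using the earlier visit multiplies the variance by 1 − ρ²m, where ρ is the between-visit correlation after baseline adjustment and m the fraction missing.
- ρ = 0.5, m = 0.10: 1 − 0.25 × 0.10 = 0.975
- ρ = 0.7, m = 0.15: 1 − 0.49 × 0.15 = 0.927

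The saving is about 2% to 7%. If 0.5 to 0.7 are instead raw correlations shared with baseline, ρ = (r − r²)/(1 − r²) is 0.33 to 0.41, and the saving falls to about 1% to 3%.

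**The case against.** The strongest reply is that section 7.1 does not say what it is taken to say. It does not order one regression per visit, the list of model terms need not be exhaustive, and a likelihood ratio test suits a mixed model too. Visit terms and covariance structure are commonly left to an analysis plan. It is true that the per-visit form is a reading. It is nonetheless the plain one: the protocol names the analysis set and the covariates, and baseline and arm alone make no use of intermediate visits.

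The missing-data sensitivity analyses might also extend to secondary outcomes, since section 7.1 says these are analysed similarly to the primary one. That link is arguable, because the same sentence then narrows the set to available patients.

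Patients and quality-of-life assessors are blinded (sections 3.1 and 3.5.4), which makes drop-out that differs by arm less likely. This stands, and it is one reason why the point is small.

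A reader might also infer three stronger things that the protocol does not support:
- **That NYHA is stated to be modelled linearly.** The model sentence does not name NYHA. It is only grouped with the quality-of-life measures, with no other method given.
- **That EQ-5D lacks a single treatment effect.** Section 7.2 combines its visits into a baseline-adjusted 24-month QALY, with zero utility at death and weighting for censoring.
- **That pooling visits brings a far larger gain in precision.** A three-visit average has 20% to 33% less variance than a single visit, but it estimates a different quantity. It is no gain for the 24-month contrast.

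**Conclusion.** The point holds as a modest improvement, not as an error that undermines the trial. On its plain reading, the specified secondary analysis is open to a bias of roughly 0.01 to 0.08 SD at 24 months with 10% to 15% loss. The lower part of that range (0.01 to 0.03) applies when baseline is as strongly correlated with later scores as those scores are with each other. All these values are below one standard error.

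The bias is conditional. The range assumes drop-out that depends on post-surgery scores in one arm only, and nothing in the protocol says this will occur. It would be wrong to conclude that the available-patient analysis is valid only when missingness is unrelated to any score: dependence on baseline is tolerated, and equal dependence with equal loss in both arms gives about zero bias.

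Using the earlier visits removes the bias under missing-at-random and trims the 24-month variance by about 2% to 7%. Only SF-36, visit-level EQ-5D and, by its grouping, NYHA are touched. The co-primary QALY analysis is unaffected.

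**What to change.** In section 7.1:
- Analyse SF-36 and visit-level EQ-5D with a likelihood-based repeated-measures model. Include baseline, visit, arm and arm-by-visit, with unstructured covariance and all available post-baseline scores. Report the 12- and 24-month contrasts.
- Say how deaths enter. The note to Appendix 2 expects 5% post-surgical mortality, and a missing-at-random model would otherwise implicitly project scores for patients who have died. State that scores after death are not treated as missing data of that kind, for example by interpreting the contrasts alongside survival.
- State that the missing-data sensitivity analyses cover these outcomes.
- State that NYHA class is analysed by proportional-odds regression adjusted for baseline class.

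The cost is analysis programming, with no new visits, data or patients. The small downside is a slightly more complex model that relies on missing-at-random.
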